3.3.2 Inclusion criteria

1. Diagnosis of CLL established according to IWCLL criteria ([R10-4429](#)) and documented within medical records.
2. Relapsed or refractory CLL pre-treated with at least one prior line of systemic therapy for CLL.
3. Indication for treatment consistent with IWCLL criteria, i.e. at least one of the following criteria should be met
 - a) Evidence of progressive marrow failure as manifested by the development of, or worsening of, anaemia and/or thrombocytopenia.

- b) Massive (i.e., lower edge of spleen ≥ 6 cm below the left costal margin) or progressive or symptomatic splenomegaly.
 - c) Massive nodes (i.e., ≥ 10 cm in longest diameter) or progressive or symptomatic lymphadenopathy.
 - d) Progressive lymphocytosis in the absence of infection, with an increase in blood ALC $\geq 50\%$ over a 2-month period, or a lymphocyte doubling time (LDT) of < 6 months (as long as initial ALC was $\geq 30000/\mu\text{L}$).
 - e) Autoimmune anaemia and/or thrombocytopenia that is poorly responsive to corticosteroids or other standard therapy.
 - f) Constitutional symptoms, defined as any one or more of the following disease-related symptoms or signs:
 - i. unintentional weight loss of 10% or more within the previous 6 months
 - ii. significant fatigue (i.e. ECOG PS 2 or worse; inability to work or perform usual activities)
 - iii. fevers higher than 100.5°F or 38.0°C for ≥ 2 weeks without other evidence of infection
 - iv. night sweats for > 1 month without evidence of infection
4. Clinically quantifiable disease burden defined as at least one of the following:
- a) either ALC $> 10\,000/\mu\text{L}$, or
 - b) measurable lymphadenopathy (at least one node > 1.5 cm in short diameter on CT or Magnetic Resonance Imaging (MRI) or
 - c) quantifiable bone marrow infiltration documented in a bone marrow biopsy during screening
5. Minimum interval to prior CLL treatment in line with the following requirements:
- a) Last dose of a cytotoxic drug, a monoclonal antibody targeting CD20, or an investigational drug to treat CLL at least 1 week prior to the first dose of ibrutinib.
 - b) Last dose of idelalisib at least 48 hours prior to the first dose of ibrutinib.
 - c) Last dose of alemtuzumab at least 4 weeks prior to the first dose of ibrutinib.

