3.3.3 Exclusion criteria

1. Known transformation of CLL to an aggressive B-cell malignancy at the time of screening (e.g. large B-cell lymphoma, Richter's syndrome). Patients with Richter's Syndrome that has resolved ≥ 2 years from signing are eligible.
2. Prior allogeneic stem cell transplant within one year or active graft vs. host disease.
3. History of a non-CLL malignancy except for adequately treated in situ, stage 1 or 2 carcinoma in CR after appropriate treatment, or any other cancer that has been in CR for ≥ 2 years after end of cancer treatment.
4. Active, uncontrolled autoimmune cytopenia. Patients with autoimmune cytopenia which is controlled with corticosteroids at doses of ≤ 20 mg prednisolone or equivalent may be enrolled.
5. Previous CLL treatment with a CD37-targeting antibody or a CD37-antibody drug conjugate.
6. Previous treatment with ibrutinib
7. Previous treatment with another BTK-inhibitor than ibrutinib.
8. Ongoing systemic immunosuppressive therapy other than corticosteroids.
9. Active bacterial, viral, or fungal infection requiring systemic treatment at the time of study entry.
10. Human Immunodeficiency Virus (HIV) infection
11. Active hepatitis B or C as evidenced by detection of virus specific Deoxyribonucleic Acid (DNA) or Ribonucleic Acid (RNA).
12. History of stroke or intracranial hemorrhage within 6 months prior to enrollment
13. Chronic persistent atrial flutter or atrial fibrillation. Patients with intermittent atrial fibrillation may be enrolled if without episode for ≥ 6 months and without indication for anti-coagulation
14. Requirement for chronic anticoagulation with warfarin or with direct oral anticoagulants at the time of screening.
15. Chronic treatment (i.e. >7 days) with a strong CYP3A inhibitor which cannot be terminated prior to the first dose of ibrutinib. Examples include but are not restricted to: ritonavir, indinavir, nelfinavir, saquinavir, boceprevir, telaprevir, nefazodone)
16. Unstable angina pectoris, uncontrolled hypertension, uncontrolled asthma or other pulmonary disease

17. Other concomitant serious illness considered by the investigator to potentially compromise patient's safety in this trial or significant co-morbidities that would impede patients participation in the trial (examples: inability to travel to the site at prescribed intervals, inability to swallow oral medication)
18. Women who are pregnant, nursing, or who plan to become pregnant while in the trial

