5.3.3 Safety laboratory parameters

5.3.3.1 General safety laboratory parameters

Blood and urine samples have to be collected at the time points specified in the [Flow Chart](#). However, more frequent samplings may be done to perform additional safety laboratory

examinations whenever the investigator deems it necessary. Local laboratories of the sites will be used for safety laboratory assessments. Sample and handling will be performed in accordance with local site procedures.

- Hematology:** Hemoglobin, red blood count (RBC), white blood count (WBC) with differential: neutrophils, basophils, lymphocytes, monocytes, eosinophils - expressed preferably in absolute values percentages accepted (including Gumprecht shadow (Smudge Cells) and Large Unstained Cells (LUC)) and platelets
- Biochemistry:** Sodium, potassium, calcium, inorganic phosphate, creatinine, AST, ALT, Alkaline Phosphatase (AP), Lactate Dehydrogenase (LDH), Blood Urea Nitrogen (BUN), uric acid, total bilirubin. If total bilirubin is elevated, direct bilirubin should be provided.
If direct bilirubin is elevated, the following tests to assess haemolysis should be obtained in addition: direct antiglobulin test, reticulocytes, haptoglobin.
- Coagulation:** Activated Partial Thromboplastin Time (aPTT) in seconds, Prothrombin Time (PT) in seconds or International Normalized Ratio (INR) have to be measured at screening, at visit 1 of every other cycle and at the EOT visit
- Urine:** Urine pH, glucose, erythrocytes, leukocytes, protein, nitrite will be analysed by dipstick. In case of suspicion of a clinically relevant proteinuria, *i.e.* at least 2 positive results after prior negative tests, protein should be quantified in 24 hour urine
- Pregnancy test:** A pregnancy test in serum or urine needs to be obtained at the time points indicated in the Flow Chart in women of childbearing potential

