5.3.6.2 Dose limiting toxicities

All drug related AEs, including SAEs and deaths, will be carefully evaluated by investigators for DLT. Dose escalation decisions will be based on DLTs observed in Cycle 1. Dose Limiting Toxicity is defined as follows:

- Any non-hematologic AE of Grade ≥ 3 related to BI 836826 and/or ibrutinib will be considered DLT, except:
 - Infusion-related reaction, any Grade
 - Grade 3 AST- and/or ALT elevation without concomitant bilirubin elevation or any other asymptomatic Grade 3 laboratory abnormality with spontaneous recovery within 1 week
- The following hematologic AEs related to BI 836826 and/or ibrutinib will be considered DLT:
 - Grade 4 neutropenia with concomitant infection
 - Grade 4 febrile neutropenia, and Grade 3 febrile neutropenia not resolving within 72 hours with appropriate treatment (antibiotics, antivirals, antifungals, growth factor support)
 - Grade 4 thrombocytopenia with clinically significant bleeding
 - Grade 4 anemia
 - Any Grade 5 hematologic AE

Patients will be evaluable for MTD in Cycle 1 if:

- a DLT occurs at any time, or
- a minimum exposure to BI 836826 and ibrutinib has been achieved. The minimum exposure is defined as $\geq 80\%$ of the planned ibrutinib doses (since Day 1 of Cycle 1) and all planned administrations of BI 836826 in Cycle 1. If the administration in Cycle 1 on Day 15 is delayed, the DLT evaluation will be prolonged to cover 14 days after the D15 administration.

All patients who have started trial treatment, but do not meet at least one of the above criteria at the end of Cycle 1 will be evaluated for safety, but replaced for MTD evaluation.

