7.2 NULL AND ALTERNATIVE HYPOTHESES

The analyses in this trial are descriptive and exploratory. No formal statistical tests will be performed.

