Worsening of constitutional symptoms in the absence of other objective evidence of worsening of CLL will not be considered disease progression, and other causes for constitutional symptoms, e.g. infections should be considered.

Ibrutinib can mobilize CLL cells from tissues into the peripheral blood. This characteristic pharmacologic action can be prominent early in therapy, but it can also persist over time, and should not be confused with PD unless the treated patient develops other CLL-related signs or symptoms of PD. In the absence of other objective evidence of PD, lymphocytosis alone should not be considered an indicator of PD. Patients with lymphocytosis and no other evidence of PD should continue therapy until they develop other definitive signs of or the occurrence of another reason to discontinue therapy.

During therapy, anemia and/or thrombocytopenia may be difficult to differentiate from drug related effects on PLT or hemoglobin. If there is uncertainty whether there is true progression, the patient should continue study treatment and remain under close observation, e.g. with additional unscheduled assessments, which should be captured in the eCRF. If subsequent evaluations indicate CLL progression, the date of progression should be the date at which progression was first documented.

Stable Disease (SD)

For SD, the following criteria must be met:

- No evidence of new disease
- There is neither sufficient evidence of tumor shrinkage to qualify for CR/CRi/PR/PR-L nor sufficient evidence of tumor growth to qualify for definitive PD

Non Evaluable (NE)

In a patient who does not have clinical evidence for PD based on CBC/Diff, the response assessment may be NE in the following situations:

- No imaging study performed.

- Inadequate imaging quality, or missing sections which do not allow assessment of all areas in which target lesions were selected. (PD may be assigned at any timepoint regardless of the extent of missing target lesions)
- Images of liver and/or spleen missing (exception: splenectomized patient).

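### Protocol Section 5.3.3.1 requires the haemolysis tests when direct bilirubin is raised, so the usual haemolysis pattern (raised total, normal direct) does not require them

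*Protocol*

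**What the plan says.** The biochemistry entry in Protocol Section 5.3.3.1 sets a two-step rule. Step one: "If total bilirubin is elevated, direct bilirubin should be provided". Step two: "If direct bilirubin is elevated, the following tests to assess haemolysis should be obtained in addition: direct antiglobulin test, reticulocytes, haptoglobin". The second sentence gives both the trigger and the purpose of the tests.

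The same section leaves room for discretion: "more frequent samplings may be done to perform additional safety laboratory" examinations when the investigator sees a need.

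Three other parts of the protocol bear on how much the rule matters:

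- **Population.** Inclusion criterion 3e in Section 3.3.2 lists as one treatment indication: "Autoimmune anaemia and/or thrombocytopenia that is poorly responsive to corticosteroids or other standard therapy". Exclusion criterion 4 in Section 3.3.3 bars active, uncontrolled autoimmune cytopenia but makes an exception: "Patients with autoimmune cytopenia which is controlled with corticosteroids" at a capped dose may be enrolled.
- **Relatedness.** Section 5.3.6.1 asks the investigator to judge causality from all relevant factors. Section 5.3.6.2 counts an event as a DLT only if it is related to BI 836826 and/or ibrutinib.
- **Progression.** Appendix 10.2 accepts a fall in haemoglobin as progression when it is attributable to CLL, and warns: "During therapy, anemia and/or thrombocytopenia may be difficult to differentiate from drug related effects on PLT or hemoglobin".

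**The concern.** The trigger works against the purpose stated in its own sentence. Direct (conjugated) bilirubin reflects excretion by the liver. Red-cell breakdown mainly raises the indirect (unconjugated) part, which is total minus direct. A test panel meant to assess haemolysis is therefore required for the pattern that usually has another cause, and not required for the pattern that usually suggests haemolysis.

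What is at stake is the evidence available for a causality judgement. When haemoglobin falls or bilirubin rises during treatment, the candidate explanations include autoimmune haemolysis from the disease, a drug effect, and progression of CLL. The antiglobulin test, reticulocyte count and haptoglobin help to separate these. If they are missing in the patients for whom they would be informative, relatedness is judged on less information. That judgement feeds the DLT counts (Protocol Section 7.3.1 presents them for Cycle 1 and for all cycles) and the tables of drug-related adverse events (SAP Section 7.8.1.2).

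**Working it through.** No arithmetic applies and the plan gives no figure to reproduce. The check is a reading of the rule against each bilirubin pattern, followed by a search for any other provision that fills the gap.

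**Step 1: the rule as written (Protocol Section 5.3.3.1)**

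| Total bilirubin | Direct bilirubin | Usual meaning | Haemolysis tests required? |
|---|---|---|---|
| Raised | Normal, so the excess is indirect | Haemolysis pattern | No |
| Raised | Raised | Hepatobiliary or cholestatic pattern | Yes, all three |
| Normal | Not requested | – | No |

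The first two rows are reversed relative to the stated purpose. The column of usual meanings is ordinary physiology; the documents do not state it, and no outside figure is needed for it. A patient with haemolysis whose direct bilirubin is also raised would still be tested.

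**Step 2: other provisions in the supplied text**

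- The bilirubin rows of the dose-modification table (Section 4.1.4.5) ask for bilirubin monitoring, not haemolysis tests.
- The hepatic-injury definition (Section 5.3.6.1) uses total bilirubin combined with transaminases, or transaminases alone. It leads to a liver-injury checklist kept in the data-capture system and the site file. That checklist is not among the supplied documents, so its content is unknown. It is tied to the alert, and an isolated bilirubin rise does not meet the alert.
- Routine haematology and biochemistry include haemoglobin, red cell count, LDH and total bilirubin. These can raise suspicion of haemolysis. LDH is also a tumour-lysis parameter in Section 5.3.3.3, so it is not specific.
- Neither the protocol nor the SAP mentions indirect or unconjugated bilirubin, and neither sets another trigger for the three tests.

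**Step 3: can such patients be in the trial?** Yes. Criterion 3e makes autoimmune anaemia a possible treatment indication, and exclusion 4 admits steroid-controlled autoimmune cytopenia.

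**Step 4: where the missing results would be used.** They would inform relatedness under Section 5.3.6.1, including for the Grade 4 anaemia DLT in Section 5.3.6.2, and the attribution of a haemoglobin fall under Appendix 10.2.

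**The case against.** The strongest reply is that this is a slip of one word with little practical effect. Investigators may add tests, and experienced CLL physicians who see falling haemoglobin with raised LDH would probably do so. Exclusion 4 keeps out active, uncontrolled autoimmune cytopenia, and Table 3.3.2:1 sets entry limits for haemoglobin and total bilirubin. Relatedness is a judgement on all the evidence, not on three tests. For doubtful haemoglobin-based progression, Appendix 10.2 already advises continued treatment with close observation and extra assessments. Recruitment is being stopped (Section 2.1), the SAP plans an abbreviated report (Section 3), and response is no longer a listed endpoint (Protocol Section 5.1).

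Most of this stands, and it limits the point. It does not remove it: discretion is not a requirement, and the written rule directs sites to the wrong pattern.

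A reader might also infer more than the documents support:

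- **That patients with haemolysis go untested.** They are not required to be tested; the investigator may still order the tests.
- **That haemolysis results would restore the transaminase exemption from DLT.** The exemption covers a Grade 3 ALT or AST "elevation without concomitant bilirubin elevation or any other asymptomatic Grade 3 laboratory abnormality with spontaneous recovery within 1 week". For transaminases it depends on whether bilirubin is raised, not on why. The tests could matter only through relatedness.
- **That the tests would prevent false hepatic-injury alerts.** The alert is a set of laboratory thresholds, and the tests would not change whether it is met.
- **That the 28% rate of drug-related anaemia in trial 1270.1 (Section 1.2.1) measures the problem.** That figure covers anaemia already judged drug-related, with a highest grade of 3. The anaemia DLT is Grade 4, and nothing links the figure to haemolysis.
- **That the next-dose contrasts in Table 10.7:1 measure it.** They show the effect of one DLT from any cause.

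**Conclusion.** The point holds as a defect in an operative monitoring rule: the trigger in Section 5.3.3.1 contradicts its stated purpose, and no other supplied text repairs it. For an isolated indirect rise in bilirubin, the rule never requires the tests; only discretion covers these patients.

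The consequence cannot be sized in patients or events, because the documents give no rate of haemolysis. It is confined to safety monitoring and to the evidence behind relatedness and CLL attribution. The dose-toxicity model and the sample size are unaffected, and as Section 7.2 says, "No formal statistical tests will be performed", so no inference is at risk. With recruitment stopping, the effect on further dose escalation is small at most. What remains is mainly attribution in patients still on treatment, some of whom may continue to Cycle 24.

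The conclusion rests on one physiological premise (haemolysis mainly raises the indirect fraction) and on the supplied text; the liver-injury checklist was not available.

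**What to change.** The sponsor should reconcile the trigger in Section 5.3.3.1 with the purpose given in the same sentence, so that the three tests are keyed to a raised bilirubin that the direct fraction does not explain (indirect = total minus direct). Both values are already obtained whenever total bilirubin is raised.

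The cost is one phrase, communicated to sites still treating patients. It needs no new visit and no new type of test, and it changes no dose, treatment or stopping rule. One practical detail needs a decision: Table 3.3.2:1 exempts patients with diagnosed Gilbert's syndrome from the bilirubin limit. They can have an indirect rise without haemolysis, so the sponsor should state how the reworded trigger applies to them.

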5.3.3.2 Serum immunoglobulin levels

Serum immunoglobulin levels (IgA, IgG, Immunoglobulin M (IgM)) have to be analysed quantitatively at screening, at visit 1 of each other cycle (Cycle 2, 4, 6, etc...) and at the EOT visit.

5.3.3.3 Screening for laboratory evidence of Tumor Lysis Syndrome

To allow for early treatment in case TLS develops, monitoring is recommended.

After the first 50% dose of BI 836826 in Cycle1 on Day 2, the following laboratory parameters should be obtained in appropriate intervals, but at least twice within the first 24 hours after the end of infusion:

- uric acid
- potassium
- phosphorus
- calcium

- LDH
- creatinine

In case of laboratory values pointing towards laboratory signs of TLS, hospitalization, appropriate monitoring and treatment should be initiated (see also [Section 4.2.1.2.2](#)).

5.3.3.4 Virology

5.3.3.4.1 Screening for hepatitis B, hepatitis C and HIV

A local laboratory will be used.

Patients with active Hepatitis B Virus (HBV), Hepatitis C Virus (HCV) or laboratory evidence of a chronic infection have to be excluded from the trial. The same applies to patients with HIV infection or detection of a HIV infection at screening.

The following laboratory parameters have to be determined at the screening visit and reported in the eCRF: Hepatitis B Surface Antigen (HBsAG), Hepatitis B Surface Antibody (anti-HBs), Hepatitis B Core Antibody (anti-HBc), HBV DNA and HCV RNA by quantitative assays. HIV Antibody (anti-HIV).

Patients can be treated with BI 836826 if:

- HBV DNA negative
- HCV RNA negative
- HIV antibody negative

Patients who are HBc antibody positive at screening will be monitored for potential HBV reactivation by quantitative HBV DNA at visit 1 of every even course and at the EOT visit. If there is evidence for HBV reactivation, immediately discontinue BI 836826 and start appropriate treatment for HBV.

5.3.3.4.2 CMV monitoring

Monitoring of CMV has to be performed at the time points indicated in the [Flow Chart](#) at a local laboratory by quantitative Polymerase Chain Reaction (PCR) assays to detect CMV DNA. The same method and cutoff should be used for the same patients, and preferably for all patients treated at the same investigational site.

Results have to be reported in the eCRF.

5.3.4 Electrocardiogram

A 12-lead resting ECG will be performed in all patients according to the schedule in the Flow Chart. The ECG will be assessed locally for pathological results to be recorded as an AE if deemed clinically significant by the Investigator, or qualified individual delegated by the PI. Additional examinations should be done whenever the Investigator deems necessary. ECGs will be stored locally at the clinical sites and not transferred to a central lab.

5.3.5 Other safety parameters

Not Applicable.

5.3.6 Assessment of adverse events

5.3.6.1 Definitions of AEs

Adverse Event:

An AE is defined as any untoward medical occurrence in a patient or clinical investigation patient administered a pharmaceutical product and which does not necessarily have to have a causal relationship with this treatment.

An AE can therefore be any unfavourable and unintended sign (including an abnormal laboratory finding), symptom, or disease temporally associated with the use of a medicinal product, whether or not considered related to the medicinal product.

Serious Adverse Event (SAE):

A SAE is defined as any AE which:

- results in death,
 - is life-threatening,
 - requires inpatient hospitalisation or prolongation of existing hospitalisation,
 - results in persistent or significant disability or incapacity,
 - is a congenital anomaly/birth defect,
- or
- is to be deemed serious for any other reason if it is an important medical event when based upon appropriate medical judgment which may jeopardize the patient and may require medical or surgical intervention to prevent one of the other outcomes listed in the above definitions.

Life-threatening in this context refers to an event in which the patient was at risk of death at the time of the event; it does not refer to an event that hypothetically might have caused death if more severe.

AEs considered “Always Serious”:

In accordance with the European Medicines Agency initiative on Important Medical Events, Boehringer Ingelheim has set up a list of AEs, which by their nature, can always be considered to be “serious” even though they may not have met the criteria of an SAE as given above.

The latest list of “Always Serious AEs” can be found in the Remote Data Capture (RDC) A copy of the latest list of “Always Serious AEs” will be provided to you upon request. These events should always be reported as SAEs.

Every new occurrence of cancer of new histology must be classified as serious event regardless of the time since the discontinuation of the trial medication and must be reported as described in [5.3.7](#), subsections “AE collection” and “AE reporting to sponsor and timelines

Adverse events of special interest:

The term AESI relates to any specific AE that has been identified at the project level as being of particular concern for prospective safety monitoring and safety assessment within this trial, e.g. the potential for AEs based on knowledge from other compounds in the same class. AESI need to be reported to the Sponsor's Pharmacovigilance Department within the same timeframe that applies to SAE, see [Section 5.3.7](#).

The following events are considered as AESIs:

1. Hepatic injury
2. Late onset infections
3. Any AE qualifying for a DLT

Hepatic injury:

Although rare, drug-induced liver injury is under constant surveillance by sponsors and regulators and is considered an AESI. Timely detection, evaluation, and follow-up of laboratory alterations of selected liver laboratory parameters to distinguish an effect of the underlying malignancy on liver function from other causes are important for patient safety.

In patients with normal transaminases and bilirubin at baseline, a hepatic injury is defined by any of the following alterations of hepatic laboratory parameters:

- an elevation of AST and/or ALT ≥ 3 fold Upper Limit of Normal (ULN) combined with an elevation of total bilirubin ≥ 2 fold ULN measured in the same blood sample, and/or
- marked peak aminotransferase (ALT, and/or AST) elevations ≥ 10 fold ULN.

In patients with elevated transaminases and/or bilirubin at baseline in line with in- and exclusion criteria of this protocol, a hepatic injury is defined by the following alterations of hepatic laboratory parameters:

- an elevation of AST and/or ALT >5 fold ULN combined with an elevation of total bilirubin >2 fold ULN measured in the same blood sample, and/or
- marked peak aminotransferase (ALT, and/or AST) elevations ≥ 10 fold ULN.

These lab findings constitute a hepatic injury alert and the patients showing these lab abnormalities need to be followed up according to the "Drug Induced Liver Injury (DILI) checklist" provided via the RDC-system and within the ISF.

Work-up as outlined in the "DILI-checklist" will serve to confirm the initial abnormality, obtain a comprehensive history and medical assessment, assess the severity of liver injury, evaluate data for potential alternative causes and decide on management of trial drug. Follow up of the potential DILI case should be initiated within 48 hours of the initial laboratory alert, or as soon as possible if timelines cannot be met. When performing all of the required examinations, the investigator may use clinical judgement, based on the patient's disease, comorbidities, clinical situation, past viral infections and risk for reactivation, exposure, prior therapy for malignant disease, co-medications and other factors as applicable. The sequence of tests in the DILI checklist may be used as guidance. The findings from the hepatic imaging (including comparison to prior imaging if available) must be made available as soon as

possible as part of the AE reporting process and/or on the respective CRF pages. In the event the etiology of the abnormal liver test results is not identified based on the imaging (e.g. biliary tract, pancreatic or intrahepatic pathology), the “DILI checklist” must be completed. Virus reactivation should be assessed by viral load and PCR testing where possible. Diagnostics for auto-immune hepatitis, Wilson’s disease and hemochromatosis can be completed at the end of all assessments, as these examinations will not change within a short time period but can be considered proof of a long persisting chronic condition. In case a laboratory parameter of the DILI checklist cannot be performed, the investigator should provide a comment including a brief assessment of the relevance of this parameter for the overall evaluation of DILI.

In case of clinical symptoms of hepatic injury (icterus, unexplained encephalopathy, unexplained coagulopathy, right upper quadrant abdominal pain, etc.) without lab results (ALT, AST, total bilirubin) available, the investigator should make sure these parameters are analysed, if necessary in an unscheduled blood test. Should the results meet the criteria of hepatic injury alert, the procedures described in the DILI checklist should be followed.

If the investigator determines any AESI is related to study drug, the administration of the study drug must be managed according to [Section 4.1.4](#) of the protocol.

Late onset infections with onset date during the extended follow-up period and considered clinically relevant and/or BI 836826 related by the investigator are also AESIs.

Any AE qualifying for a DLT:

No other AESIs have been defined for this trial.

Severity of AEs:

The severity of AEs should be classified and recorded in the (e)CRF according to the CTCAE v 4.0.

Causal relationship of AEs:

Medical judgment should be used to determine the relationship considering all relevant factors, including pattern of reaction, temporal relationship, de-challenge or re-challenge, confounding factors such as concomitant medication, concomitant diseases and relevant history.

Yes: There is a reasonable causal relationship between the trial medication administered and the AE.

No: There is no reasonable causal relationship between the trial medication administered and the AE.

The causal relationship must be provided by the Investigator for the trial medication BI 836826 investigational drug and for the backbone therapy, ibrutinib.

The reason for the decision on causal relationship needs to be provided on the SAE form (if applicable).

